12.1.2 Safety analysis set

The safety analysis set will include all subjects who received at least one dose of randomised study medication and who provide any safety records. Subjects who were dispensed the same wrong treatment for the entire treatment period (ie, those randomised to dapagliflozin 10 mg but actually given placebo, or vice versa) will be counted in the treatment group for which they received medication.

12.2 Methods of statistical analyses

12.2.1 Demographics and baseline characteristics

Descriptive summaries of demographics and baseline characteristics will be presented by treatment group and for all subjects combined using the full analysis set.

12.2.2 Efficacy analysis

For the primary variable, the change from baseline in HbA1c to Week 24, each pair wise treatment group comparison will be tested at a significance level of approximately 0.027, according to Dunnett's method, in order to maintain an overall Type I error rate <0.050 for the primary objective.

A hierarchical closed testing procedure will be used to control the Type I error rate across the primary and key secondary objectives within each dapagliflozin treatment group. Key secondary objectives are to compare the effects of each dose of dapagliflozin versus placebo after a 24-week double-blind treatment period by evaluation of:

1. The change from baseline in FPG at Week 24 (LOCF).
2. The change from baseline in total Body weight at Week 24 (LOCF).

The statistical testing of the primary and key secondary efficacy endpoints will proceed in a sequential manner, to control the type I error rate within each dapagliflozin group at the 0.05 level. Specifically, the significance or non-significance of the treatment comparisons for the primary efficacy endpoint will determine which, if any, statistical inferences are made for the key secondary efficacy endpoints. Only those dapagliflozin groups significantly superior to placebo for the primary efficacy endpoint will have statistical inference vs placebo for the first key secondary endpoint, (1). Then, the testing for the other key secondary efficacy endpoints will proceed so that the significance or non-significance of the treatment comparisons for (1) will determine which, if any, statistical inferences are made in treatment comparisons for (2). If a result for one of the dapagliflozin treatment groups is not significant, statistical inference ends at

that endpoint and no statistical inference will be applied to the subsequent key secondary endpoints for that treatment group.

If at least one of the primary comparisons between a dapagliflozin treatment group and the placebo treatment group is significant at the 0.027 level for the primary endpoint, all statistical tests for the two key secondary efficacy endpoints will be performed and nominal p-values will be reported. However, in order to protect the global type I error rate of the hierarchical testing procedure, the interpretation of the statistical significance of treatment comparisons for each key secondary efficacy endpoint will be done using the step-wise procedure described above.

Other secondary outcome variables and exploratory outcome variables shall provide supportive efficacy and safety information regarding the differences between the treatment groups. For other secondary efficacy variables, supportive statistical test will be made at nominal significance level 0.05 and nominal p-values will be reported.

Unless otherwise specified, for all changes (or percent changes) from baseline to a specific time point post-baseline as well as for glycemic therapeutic response definitions, analyses will be based on measurements available at that time point or the last post baseline measurement prior to the time-point, if no measurement is available at that time point, ie, last observation carried forward (LOCF). For rescued subjects, values collected after initiation of rescue medication will not be considered in calculating the LOCF values for glycemic endpoints.

The time course of all continuous variables will be presented using standard descriptive summary statistics.

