12.3 Determination of sample size

Each pairwise treatment group comparison will be tested at a significance level of approximately 0.027, according to Dunnett's method, in order to maintain an overall type I error rate < 0.050 for the primary objective. To detect a difference of 0.5% between each dapagliflozin group versus placebo for changes in HbA1c from baseline to Week 24, assuming a SD = 0.9%, and at a two-sided significance level of 0.027, 80 evaluable subjects are needed in each treatment group to provide 90% power. The assumed SD=0.9 is considered to be appropriate based on Japan Phase IIb study and Global monotherapy Phase III study result where SD was approximately 0.52% and 0.91%, respectively. Assuming that approximately 5% of the subjects will not have a post-baseline efficacy measurement, 85 subjects per treatment group (255 subjects total) are planned for randomization.

The sample size for this study was selected to be consistent with the research hypothesis as described in Section 1.2.

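### Testing both doses on HbA1c at 0.027 is valid but gives up power: P(both doses significant) is about 83%, against 87–89% with a step-down rule that protects the key secondaries

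*Protocol*

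**What the plan says.** Protocol section 12.2.2 states that "each pair wise treatment group comparison will be tested at a significance level of approximately 0.027", by Dunnett's method, and gives the reason: "in order to maintain an overall Type I error rate <0.050 for the primary objective". The synopsis repeats this, and section 12.3 opens with the same rule: "Each pairwise treatment group comparison will be tested at a significance level of approximately 0.027". A later paragraph of 12.2.2 again names 0.027 as the level for success on the primary endpoint. No section allows the second dose a higher level once the first has succeeded.

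Section 12.2.2 also says that "A hierarchical closed testing procedure will be used to control the Type I error rate across the primary and key secondary objectives". The same sentence goes on to confine that procedure to each dose separately. It runs from HbA1c to FPG to body weight within a dose, and a dose that fails one step gets no inference on the later ones.

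Section 12.3 plans "To detect a difference of 0.5% between each dapagliflozin group versus placebo for changes in HbA1c from baseline to Week 24", "assuming a SD = 0.9" percent, and concludes that "at a two-sided significance level of 0.027, 80 evaluable subjects are needed in each treatment group to provide 90% power". That power is per comparison. No power is stated for confirming both doses.

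**The concern.** The primary objective concerns each dose against placebo, so the outcome in which both doses succeed matters. By the closure principle, once one dose is significant at the Dunnett level the joint null hypothesis is rejected. Only the other dose's own null remains, and it can be tested at 0.05 without raising the error over the two HbA1c comparisons above 5%. The single-step rule does not use this.

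Under the present text, a dose with an HbA1c p-value between 0.027 and 0.05 fails even when the other dose has already succeeded, and it then loses all inference on FPG and weight.

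**Working it through.** **Inputs.** Difference 0.5 for both doses, SD 0.9, 80 evaluable per arm, two-sided 0.027, 5% without a post-baseline value (12.3). Allocation is 1:1:1 (3.1.4), so the two contrasts share the placebo arm and have correlation 0.5.

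**1. The plan's own figures.**
- Sample size: n = 2(z₀.₉₈₆₅ + z₀.₉₀)² × SD²/difference² = 2 × (2.2115 + 1.2816)² × 0.81/0.25 = 79.07, so 80 per arm.
- Loss: 80/0.95 = 84.2, so 85 per arm.
- Power: the standardised effect is 0.5/(0.9 × √(2/80)) = 3.514. Power is 90.4% by the normal approximation and 90.0% by noncentral t.
- Dunnett level for two contrasts with correlation 0.5: 0.0270.

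All of these agree with the protocol.

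**2. Both doses, HbA1c only.** Numerical integration over the shared placebo mean and pooled variance, checked by simulation:

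| Rule | P(both) | P(at least one) | Power per dose |
|---|---|---|---|
| 0.027 for each dose | 83.3% | 96.7% | 90.0% |
| Step-down: 0.027, then 0.05 | 89.0% | 96.7% | 92.9% |

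Per-dose power is the mean of the two probabilities: (83.3 + 96.7)/2 = 90.0 and (89.0 + 96.7)/2 ≈ 92.9. The gain of about 5.6 points is the chance that one dose passes at 0.027 and the other has p between 0.027 and 0.05. Step-down familywise error over the two HbA1c tests is 5.0% with both doses null, 4.6% with one null and the other at 0.5, and 5.0% with one null and the other very effective.

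**3. Adding the key secondaries.** Suppose dose A surely passes HbA1c, A's FPG null is true, and B's HbA1c null is true. With both tests at 0.027, the chance of a false rejection is at most 1 − 0.973² = 5.3% (simulated 5.2–5.3% for endpoint correlation 0 to 0.7). If B is tested at 0.05 while A goes on to FPG at 0.027, it is about 1 − 0.95 × 0.973 = 7.6% (simulated 7.4–7.6%). Plain step-down on HbA1c therefore cannot simply be added to the existing FPG and weight sequence.

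**4. Release only after all three endpoints.** Keep 0.027 down HbA1c, FPG and weight within each dose. If one dose passes all three, test the other dose's sequence at 0.05.
- *Nulls in both doses.* A release requires a dose to pass one of its own true nulls, so a false rejection has already occurred at 0.027. The familywise error equals that of 0.027 throughout, at most about 5.2–5.3%.
- *Nulls in one dose only.* The fixed sequence in that dose keeps the error at or below 5%.
- *Power.* The 5.6-point gain is kept only when the first dose also passes FPG and weight. Treating the endpoints as independent, power of 79% each gives 83.3 + 5.6 × 0.79² = 86.8%. Power of 99% each gives 83.3 + 5.6 × 0.99² = 88.8%. So P(both) is about 87–89%, and P(at least one) does not change.

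**5. Sensitivity of P(both), single-step against plain step-down.**
- SD 0.91: 82.3% and 88.2%
- SD 0.8: 92.5% and 95.5%
- SD 0.7: 97.9% and 98.9%
- SD 0.52: both above 99.9%
- 85 evaluable per arm: 86.1% and 91.0%
- True difference 0.6 for both doses: 95.7% and 97.6%
- True differences 0.4 and 0.5: about 68% and 77%

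**The case against.** The strongest case against is that nothing here is wrong. The level is the correct Dunnett level, the error goal for the primary objective is met, and the sample size matches. That stands: this is lost efficiency under a valid rule.

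A reader might infer that the protocol contradicts itself by naming a closed procedure and then testing both doses at 0.027. The text does not support this. The closed procedure is confined to the endpoints within a dose, Dunnett's method covers the two doses, and closure across doses is never promised.

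A reader might also infer that plain step-down is free. It is for HbA1c alone, but step 3 shows that it raises the error across doses and endpoints to about 7.5%. The protocol claims 0.05 only within each dose, yet its present rule comes close to control over both doses, and that should not be weakened.

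Single-step Dunnett is sometimes preferred because its simultaneous intervals (97.3% each here) match the test. Section 12.2.2.1 plans 95% intervals, so that advantage is not being used.

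Finally, the benefit depends on a large SD. Section 12.3 cites about 0.52 from the Japan Phase IIb study and 0.91 from the global study. Sections 1.1 and 3.2.2 report placebo-corrected reductions above 0.5% at both doses, so the 0.4 scenario is below the protocol's own evidence. This limits the size of the gain, but 0.9 is the value the sponsor chose for planning.

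**Conclusion.** The current test is valid, and there is no internal contradiction. It does leave power unused for confirming both doses: at the planning values, P(both) is about 83%, against 89% with step-down on HbA1c alone and about 87–89% with the version that also protects FPG and weight. The chance of at least one success does not change.

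These figures assume an equal 0.5 effect for both doses and an SD of 0.9. The 87–89% range also assumes 79–99% power for each of FPG and weight, which the protocol does not give. With an SD near 0.52 the gain is negligible.

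The error comparison takes 0.027 as the level carried to FPG and weight. Section 12.2.2 gives no number for those tests and refers only to 0.05 control within a dose. On that reading, the revised rule never loses a rejection that the present rule makes. If 0.05 was meant for FPG and weight, that would not hold for those tests, but the error over the two FPG comparisons would already be about 9.1% when both doses surely pass HbA1c.

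This is an improvement worth making, not the correction of an error.

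**What to change.** In section 12.2.2 and the synopsis, state that each dose is tested at 0.027 down HbA1c, FPG and body weight in that order, and that if one dose is significant on all three, the other dose's sequence is tested at 0.05. The sample size in 12.3 stays. Its sentence on the 0.027 level should refer to the step in 12.2.2.

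If strict 5% control across both doses and all three endpoints is wanted, start at 0.025 per dose (2 × 0.025 = 0.05). The 0.027 wording in 12.3 must then change too, and P(at least one) falls by about 0.2 points, from 96.7% to 96.5%.

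Either version must be fixed before unblinding. The cost is wording only: no added subjects, visits or data, and the planned 95% intervals can stay.

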12.2.2.1 Primary efficacy analysis

The change in HbA1c from baseline to Week 24 (LOCF), will be analyzed by an analysis of covariance (ANCOVA) model including treatment group and gender as fixed effect and baseline as covariate. The ANCOVA model will be used to derive a least squares estimate of the treatment difference with 95% confidence interval and corresponding 2-sided p-value.

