3.2 Rationale for study design, doses and control groups

3.2.1 Study design and regulatory requirement

The current study is designed to demonstrate the efficacy and safety of dapagliflozin versus placebo in Japanese subjects of T2DM who have inadequate glycemic control with diet and exercise.

Placebo lead-in period is set to remove any bias regarding placebo effect. Subjects who received ongoing medical treatment for diabetes within 6 weeks of enrolment, except for TZD (single oral anti-diabetic agent or two agents with less than half of the approved maximal dose for each agent) will complete a 6-week washout period, and 4 weeks of placebo lead-in for a total washout period of 10 weeks to eliminate effects of the prior therapy. The reason for 10 weeks of washout is as follows:

- (a) Adequate washout of all prior oral anti-diabetic agents and their pharmacodynamic effects.
- (b) Stabilization of HbA1c after discontinuation of any oral anti-diabetic agents takes 8-12 weeks. 10 weeks of washout allows for an adequate stabilization of HbA1c after washout of oral anti-diabetic agents except for TZDs prior to randomization of subjects to dapagliflozin versus placebo treatment arms in this study.

The Follow-up period is set to examine the reversibility of potential AE and laboratory values after taking the last dose.

This study has standard design features for a confirmatory Phase III diabetes study (eg, multi-centre, randomised, double-blind, parallel group) and incorporates the relevant features of the [Japanese Guideline on Clinical Evaluation methods on Oral Hypoglycemic Agents](#) which was issued 9th July 2010 with regard to duration of treatment, choice of study population, and choice of outcome variables.

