5.2 Subject enrolment and randomisation

Procedures for enrolment

The Principal Investigator will:

1. Obtain signed informed consent from the potential subject before any study specific procedures are performed.
2. Perform enrolment call in Interactive Web Response System (IWRS).
3. Assign potential subject a unique enrolment number “E43XXYYY”, which is composed of 4 digits (43XX) of centre number and 3 digits (YYY) of consecutive number in order of enrolment registration at each study site.
4. Determine subject eligibility. See Sections 4.1 and 4.2.
5. Perform drug allocation call for assigning Placebo Lead-In at Visit 4 in IWRS.

Routines for this will be described in the IWRS user manual that will be provided to each centre.

Procedures for randomisation

The randomisation list will be generated at AstraZeneca using the global randomisation system (GRand). The randomization will be done in balanced blocks and stratified according to gender (male, female) and HbA1c at Visit 5 category ($\geq 6.5\%$ and $\leq 7\%$, $> 7\%$ and $\leq 10\%$).

Assign eligible subjects with a unique randomisation code (patient number) through IWRS at Visit 6. (Randomisation codes will be assigned strictly sequentially as subjects become eligible for randomisation.)

Routines for this will be described in the IWRS user manual that will be provided to each centre.

If a subject withdraws from participation in the study, then his/her enrolment/randomisation code cannot be reused.

Randomisation codes will be assigned strictly sequentially as subjects become eligible for randomisation.

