12.2.2.2 Key secondary variables

The changes from baseline to Week 24 (LOCF) in FPG and total body weight will be analyzed and presented in similar way as the primary efficacy analysis described in Section [12.2.2.1](#).

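### The ANCOVAs for FPG, body weight and the other non-HbA1c continuous endpoints leave out the HbA1c category used to stratify randomisation, at a small cost in precision

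*Protocol*

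**What the plan says.** Protocol section 5.2: "The randomization will be done in balanced blocks and stratified according to gender (male, female) and HbA1c at Visit 5 category". The two HbA1c categories are 6.5% to 7%, and above 7% up to 10%. Section 3.1.4 caps the lower category at about 25% of randomised subjects.

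Section 12.2.2.1 specifies for HbA1c an ANCOVA "model including treatment group and gender as fixed effect and baseline as covariate". Section 11.1.1 takes baseline from Visit 6, one week after the value that defines the stratum.

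Section 12.2.2.2 states that the changes "in FPG and total body weight will be analyzed and presented in similar way as the primary efficacy analysis". Section 12.2.2.3 applies a similar model to SBP, waist circumference, lipids, insulin, C-peptide, glycoalbumin and percent change in weight. It also covers subgroups defined by SBP, BMI and HbA1c. Its logistic models for proportions are fitted within each treatment group and adjust for gender and a baseline variable, with baseline HbA1c given as the example.

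**The concern.** One stratification factor, gender, is carried into the model. The other is not, and no reason is given. For HbA1c this hardly matters, because the continuous baseline stands in for the category. For FPG, body weight and the remaining non-HbA1c variables, the baseline is most naturally the variable's own value, and no HbA1c term is named.

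Stratified randomisation balances the HbA1c category across arms, so the treatment difference really does vary less from trial to trial. An ANCOVA without the factor leaves the variance it explains in the error term, and the reported standard error does not show the gain. The tests are then conservative to the extent that the factor is prognostic.

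FPG and body weight are the two key secondary endpoints, and under section 12.2.2 FPG must succeed before weight is tested. Section 12.3 states power for HbA1c only, so no margin is stated for either.

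**Working it through.** **1. The plan's sample size.** Inputs from section 12.3: "To detect a difference of 0.5% between each dapagliflozin group versus placebo for changes in HbA1c", "assuming a SD = 0.9" (%), and "two-sided significance level of 0.027, 80 evaluable subjects are needed in each treatment group to provide 90% power".

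- n per group = 2(z₀.₉₈₆₅ + z₀.₉₀)² × SD²/δ² = 2 × (2.2115 + 1.2816)² × 0.81/0.25 = 79.1, rounded up to 80.
- Power at 80 per group is 90.4% by the normal approximation and 89.9% by the noncentral t.
- For the allowance that "approximately 5% of the subjects will not have a post-baseline efficacy measurement": 80/0.95 = 84.2, rounded up to 85; 3 × 85 = 255.
- Two-sided Dunnett with two comparisons sharing a control (correlation 0.5): critical value 2.212, per-comparison level 0.02696, which agrees with 0.027.

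The plan's figures reproduce. They use an SD of 0.9% with no stated reduction for covariates, so they do not depend on the omitted term.

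**2. General size of the omission.** If the omitted term has partial R² given the other terms, the ratio of the standard error without it to that with it is 1/√(1 − R²). The documents give no R², so the following is a range of assumptions.

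| Assumed partial R² | SE wider by |
|---|---|
| 0 | 0% |
| 0.01 | 0.5% |
| 0.02 | 1.0% |
| 0.05 | 2.6% |
| 0.10 | 5.4% |

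**3. Simulation of this design.** Setup: 600 replicates; stratified blocks, 1:1:1, 80 per group; 25% in the low category. Assumed inputs, none from the documents: Visit 5 HbA1c normal with mean 7.6 and SD 0.8, restricted to 6.5 to 10%; Visit 6 equal to Visit 5 plus noise of SD 0.15; baseline FPG correlated about 0.6 with HbA1c; residual SDs 0.85% (HbA1c), 25 mg/dL (FPG) and 2.2 kg (weight). Each ANCOVA was fitted with and without the stratum.

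| Assumed independent effect per 1% HbA1c (FPG change; weight change) | FPG: SE wider without stratum | Weight: SE wider without stratum |
|---|---|---|
| none | −0.03% | −0.02% |
| 3 mg/dL; 0.3 kg | 0.08% | 0.23% |
| 8 mg/dL; 0.6 kg | 0.64% | 0.88% |
| 15 mg/dL; 1 kg | 2.06% | 2.28% |

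The first row shows the cost of adding a useless term: 0.02 to 0.03% in the standard error. For the primary HbA1c model, adding the stratum makes the standard error about 0.1% larger, because continuous baseline HbA1c already carries the information.

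**4. What a larger loss would require.** A partial correlation of 0.3 gives 1/√(1 − 0.09) = 1.048, or 4.8% wider, worth 240 × 0.09 = 21.6 subjects. For a two-level factor with 25% in one level, the strata would have to differ by 0.3/√(0.25 × 0.75) = 0.69 residual SDs after adjustment for gender and own baseline. With fewer subjects in the low category the difference would have to be larger still.

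**The case against.** The strongest case against is that no promise of the design is broken. The treatment estimates are unbiased, any error in the tests is conservative, the sample size stands, and no power is claimed for the secondary endpoints. All of this is correct and keeps the point small.

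It can also be said that the SAP may settle the covariates, since the secondary analyses are described only as similar to the primary. That has some force. But the protocol itself names the model terms and includes one stratification factor without the other, so the text can be corrected where it stands.

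Baseline FPG and baseline glycoalbumin are themselves glycaemic measures and carry part of the HbA1c information. This also stands, and is one reason why the likely loss is small.

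A reader might go further and infer that the primary analysis loses precision. The documents do not support this: its covariate is HbA1c itself, measured a week after the stratifying value.

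A reader might also infer that leaving out wash-out status is the same kind of fault, because section 3.2.1 says "Stabilization of HbA1c after discontinuation of any oral anti-diabetic agents takes 8-12 weeks" and washed-out subjects are randomised at week 10. But wash-out status was not used to stratify, so design and analysis do not disagree. The same section calls 10 weeks adequate. Randomisation balances the status in expectation, and the standard error already allows for chance imbalance. Under assumed inputs (30% washed out, shift in HbA1c change of 0.2% or 0.4%), omitting both stratum and wash-out status widens the HbA1c standard error by about 0.3% or 2%. That would be an optional gain in efficiency. The documents give neither the washed-out share nor any drift.

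**Conclusion.** The point holds for the non-HbA1c continuous endpoints: a factor used to stratify randomisation has no counterpart in their ANCOVA. This rests on reading baseline as the endpoint's own baseline, which is the natural reading but is not spelled out.

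The consequence depends on whether HbA1c predicts these endpoints beyond their own baseline. Where it does, standard errors are too wide by about 0 to 2% under plausible assumptions; where it does not, nothing is lost. The 4.8%, or roughly 22 subjects, that follows from a partial correlation of 0.3 has no support in the documents. This is a minor loss of efficiency that is easily avoided. It is not a threat to validity, to the primary result or to the stated power.

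**What to change.** In section 12.2.2.2, and for the non-HbA1c continuous variables in section 12.2.2.3, add the Visit 5 HbA1c stratum as randomised to the ANCOVA, or continuous baseline HbA1c instead, alongside treatment, gender and the endpoint's own baseline. State this before unblinding. The cost is one sentence and one degree of freedom out of about 240, with data already collected.

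Do not extend the change to every model:

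- The primary HbA1c model gains nothing from the extra term.
- The analyses in subjects with baseline HbA1c of at least 7.5% or at least 7% contain almost nobody from the lower stratum, so the term would be close to inestimable.
- The HbA1c responder models already adjust for baseline HbA1c. All the logistic models are fitted separately in about 80 subjects per group, so added terms cost more there, especially if rescue events are few.

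Wash-out status may be prespecified as an additional covariate if the sponsor expects it to be prognostic, but no correction is needed on that account.
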